3.7 SURGICAL GUIDELINES

Patients will undergo targeted biopsies of the prostate prior to treatment and after MRI and 18F-DCFPyL imaging. Biopsies and fiducial placement will be performed at the Clinical Center by an interventional radiologist or member of the urology service. Prior to undergoing the procedure, patients will be screened for any contraindications such as significant thrombocytopenia or elevated PT/PTT.

Patients undergo preparation identical to that of standard prostate biopsy in that antibiotics consistent with the current standard of care is taken prior to the procedure. On the morning of the procedure, patients self-administer an over-the-counter saline enema. Patients may have a light meal for breakfast on the day of the procedure. Patients undergo pre-procedural assessment including verification of prophylactic regimen described above and normal temperature and vitals. The patient is positioned on a routine hospital gurney in the right or left decubitus position with the legs flexed. A transrectal ultrasound probe is advanced into the rectal vault, a 3D prostate volume is obtained and 10 mL of 1% lidocaine is administered transcutaneously under ultrasound guidance along the posterolateral margins of the prostate to achieve local anesthesia.

Standard comprehensive prostate biopsies will be performed if not performed within the past 4 months and additional biopsies will be targeted to the region of the prostate corresponding to the area of greatest likely tumor involvement as determined by imaging (MRI). Research biopsy samples will only be obtained from areas of the prostate with greatest likelihood of tumor involvement as determined by imaging (MRI and 18F-DCFPyL) or from an area that was dominant on pre-treatment imaging and biopsy confirmed to be malignant. A maximum of 4 regions of abnormality on MRI and 18F-DCFPyL will be targeted for research biopsies. Diagnostic biopsies will be analysed by the Laboratory of Pathology as per standard clinical care.

If possible, radiotherapy fiducial markers (Calypso markers preferred) will be placed as per the current standard of care during the same procedure. In general, 3-5 fiducial markers are placed in the prostate at the same time as a biopsy procedure to assist with treatment alignment. If a patient has indwelling fiducials from a prior radiotherapy treatment, additional fiducials do not need to be placed unless required for proper positioning.

3.8 RADIATION THERAPY GUIDELINES

3.8.1 Treatment Planning

Target definition: tumor will be defined by MRI, and 18F-DCFPyL, which will be fused to the treatment planning CT. For 18F-DCFPyL, regions of tumor recurrence will be defined based on a standardized uptake value (SUV) above the SUV mean of the blood pool, with exceptions made for physiologic uptake.

3.8.2 Target volume definitions

Treatment planning definitions

GTV: gross tumor volume

CTV: clinical target volume

PTV: planning target volume

Arm 1: tumor only treatment

GTV lesion(s): image defined tumor (CT, MRI, 18F-DCFPyL (biopsy confirmed))

PTV lesion(s): GTV lesion + 3 mm posterior and superior margin and 3-5 mm margin in all other dimensions (inferior, lateral, anterior) on the GTV lesion(s).

Arm 2: Prostate + tumor

Brachytherapy or tumor (Gleason > or = to 6) identified in regions outside of areas defined by imaging.

GTV lesion(s): image defined tumor (CT, MRI, 18FDCFPyL (biopsy confirmed))

PTV lesion(s): GTV lesion + 3 mm posterior and superior margin and 3-5 mm margin in all other dimensions (inferior, lateral, anterior) on the GTV lesion(s).

CTV prostate: The entire prostate as visualized on MRI and CT. The entire or partial seminal vesicle may be included in the CTV prostate if there is concern for invasion on MRI, biopsy, or recurrent tumor is located adjacent to the root of the seminal vesicle.

PTV prostate: 3 mm posterior and superior margin and 3-5 mm margin in all other dimensions (inferior, lateral, anterior) on the CTV prostate. In some instances, an additional 1-2 mm margin may be added to the seminal vesicles if substantial motion is documented on serial imaging.

Dose to PTV prostate (cohort 2 only) will be prescribed to 30 Gy in 5 fractions to a minimum of 95% of the PTV prostate. In both arms (1 and 2), the escalated dose should cover a minimum of 95% of the PTV tumor. Dose will be escalated as defined in [3.1.2](#).

Table 4: Planning Target Volume (PTV)

| | Arm 1: Tumor Irradiation | | Arm 2: Prostate and Tumor Irradiation | |
|-------------------|---------------------------------|------------------|--|------------------|
| Dose level | PTV prostate | PTV tumor | PTV prostate | PTV tumor |
| Level 1 | - | 40 Gy | 30 Gy | 40 Gy |
| Level 2 | - | 42.5 Gy | 30 Gy | 42.5 Gy |
| Level 3* | - | 45 Gy | 30 Gy | 45 Gy |

* As of amendment version dates 4/13/2021 and 10/12/2021, determination has been made not to escalate to dose level 3 for both arms. Refer to section [1.2.5](#).

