1.2.4 Purpose of this study

The goal of this study is to develop an effective and tolerable strategy for salvage of locally recurrent prostate cancer following radiation. This study is distinct from prior efforts as it seeks to de-escalate therapy to uninvolved areas of the prostate gland and to limit escalation to imaging defined tumor. This study will evaluate focal re-irradiation with SBRT for locally recurrent prostate cancer. The highest dose of escalation, 45 Gy, is moderately higher than was previously tested. The dose to the remainder of the gland is reduced and will only be delivered in patients suspected of having disease in other locations in the prostate gland, namely those who have biopsy findings consistent with disease outside of the imaging identified lesion and patients who have undergone prior brachytherapy for whom MR imaging may be suboptimal. The area of focal escalation in this study will be guided by MRI findings in addition to findings from 18F-DCFPyL/CT and biopsy confirmation. We will include tissue staining for neuroendocrine markers in biopsy specimens harboring recurrent prostate cancer.

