2.3.1 Treatment Assignment Procedures

Cohorts

| Number | Name | Description |
|---------------|---------------|---|
| Cohort 1 | EBRT | Patients with locally recurrent prostate cancer after treatment with EBRT. These patients cannot have had permanent brachytherapy as part of their treatment. |
| Cohort 2 | Brachytherapy | Patients with locally recurrent prostate cancer after treatment with brachytherapy +/- EBRT. These patients must have had brachytherapy as part of their treatment. |

Arms

| Number | Name | Description |
|---------------|--------------------------------|--|
| 1 | Tumor Irradiation | SBRT will be delivered to areas of recurrent prostate cancer identified on imaging and biopsy |
| 2 | Prostate and Tumor Irradiation | SBRT will be delivered to areas of recurrent prostate cancer identified on imaging and biopsy; and a reduced dose will be delivered to the entire prostate |

Treatment Assignment

There is no randomization or stratification on this study.

Subjects in Cohort 1 will be directly assigned to Arm 1.

Subjects in Cohort 2 will be directly assigned to Arm 2.

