3 STUDY IMPLEMENTATION

3.1 STUDY DESIGN

Patients with locally recurrent prostate cancer following radiotherapy will be enrolled in this study if they have no evidence of distant metastatic disease on staging studies. If abnormalities are noted on bone scan and/or NaF PET/CT, the results of these studies will be reviewed by the PI and radiology/nuclear medicine colleagues. On a case by case basis, the likelihood of metastasis will be determined if evidence of abnormalities is visible. In general, NaF PET will be considered more sensitive. Multiparametric MRI of the prostate and 18F-DCFPyL imaging will be obtained to assess for areas of local recurrence. Patients found to have regional adenopathy that is distant to the prostate or metastatic disease at other sites on staging studies such as 18F-DCFPyL will undergo biopsy confirmation if clinically appropriate to confirm metastatic disease and will be removed from the study and replaced if metastases are confirmed. Patients deemed to have a non-metastatic local recurrence will undergo targeted (research and diagnostic) and systematic biopsies of the prostate (diagnostic) to confirm areas of recurrence and correlate imaging with pathology. Areas noted to have uptake on 18F-DCFPyL imaging will also be biopsied if they represent areas not seen on MRI. During the same procedure, fiducials to guide radiotherapy will be placed if not previously placed or visible. Approximately one week after fiducial placement or biopsy (if fiducial placement not required), patients will undergo treatment planning for SBRT.

There will be two Cohorts in this trial. Cohort 1 includes patients with prior EBRT for the treatment of prostate cancer. These patients may have received ADT with EBRT but have not received brachytherapy. Patients enrolled in Cohort 2 will have received brachytherapy of the prostate as a component of the initial radiation treatment (either alone or in combination with EBRT and/or ADT). See section [2.3.1](#).

SBRT will be delivered to areas of recurrent prostate cancer identified on imaging and biopsy (all patients, Arms 1 and 2) and a reduced dose will be delivered to the entire prostate (Arm 2). The low dose total prostate exposure is used in Arm 2 as MR imaging may be moderately compromised in after prior brachytherapy.

Table 2: Dose Levels

| | Arm 1: Tumor Irradiation | | Arm 2: Prostate and Tumor Irradiation | |

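### The protocol assigns an EBRT-only patient with biopsy-positive tumor outside the imaged lesion to Arm 1 in some sections and gives him the Arm 2 whole-prostate dose in others

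*Combined protocol and SAP*

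**What the plan says.** Section 2.3.1, the treatment assignment section, defines two cohorts by prior radiation and ties each to one arm without exception: "Subjects in Cohort 1 will be directly assigned to Arm 1" and "Subjects in Cohort 2 will be directly assigned to Arm 2". Arm 1 treats tumor only; Arm 2 adds a reduced dose to the entire prostate. Section 3.1 defines the cohorts the same way and explains the Arm 2 gland dose by poorer MR imaging after brachytherapy. The introduction to Section 10 and Section 10.4.1 also define the arms by prior radiation.

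Two other places use biopsy findings as well. Under the Arm 2 heading, Section 3.8.2 gives the criterion "Brachytherapy or tumor (Gleason > or = to 6) identified in regions outside of areas defined by imaging". Section 1.2.4, on who receives dose to the remainder of the gland, lists patients with prior brachytherapy and a separate group, "namely those who have biopsy findings consistent with disease outside of the imaging identified lesion".

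Further down, Section 3.8.2 returns to prior treatment: "Dose to PTV prostate (cohort 2 only) will be prescribed to 30 Gy in 5 fractions".

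On Cohort 1, Section 2.3.1 says "These patients cannot have had permanent brachytherapy as part of their treatment", while Section 3.1 says "These patients may have received ADT with EBRT but have not received brachytherapy".

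**The concern.** The two rules disagree on one identifiable kind of patient: prior EBRT, no brachytherapy, and tumor on biopsy outside the area seen on imaging. The targeted and systematic biopsies in Sections 2.4 and 3.1 are what would reveal this, and they may be done at baseline, when the cohort is already known from the treatment history.

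Two things depend on the answer. The first is the treatment he receives. The second is what each arm's results describe. Section 3.1.2 escalates the arms independently because toxicity is expected to differ with prior treatment, and Section 3.1.1 sets the MTD separately for each arm. If EBRT-only patients can enter Arm 2, that arm mixes the two prior-treatment groups that the design set out to separate.

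**Working it through.** The plan has no figure to reproduce here, so the check follows one hypothetical patient through each section: EBRT only, imaged lesion confirmed on biopsy, and a further core with Gleason 6 or higher outside the imaged area.

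| Protocol section | What decides | Result for this patient |
|---|---|---|
| 2.3.1 | Prior radiation | Cohort 1, Arm 1, no prostate dose |
| 3.1 | Prior radiation | Cohort 1; gland dose explained only by brachytherapy |
| 10, introduction | Prior radiation | Arm for prior EBRT |
| 10.4.1 | Brachytherapy or not | Arm for EBRT without brachytherapy (arms listed in the reverse order) |
| 3.8.2, dose prescription | Cohort 2 membership | No prostate dose |
| 3.8.2, Arm 2 line | Brachytherapy or tumor outside imaging | Arm 2 |
| 1.2.4 | Biopsy disease outside the lesion, or brachytherapy | Dose to the rest of the gland |

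Section 1.2.4 does not name Arm 2. By Tables 2 and 4, however, only Arm 2 has a prostate dose, so its description leads there.

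**Scope.** An EBRT-only patient with no tumor outside the imaged lesion is Arm 1 under every section. A patient with permanent brachytherapy is Arm 2 under every section. The conflict is confined to the group above.

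**Treatment difference.** Tables 2 and 4 show no prescribed prostate dose in Arm 1 and 30 Gy in Arm 2, at every dose level.

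**Weight of one patient.** Sections 3.1.2 and 10.4.1 use groups of 3 to 6 per level, and 2 patients with unacceptable toxicity mean the MTD is exceeded. One patient is 1/6 = 17% to 1/3 = 33% of a group.

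**Make-up of the arms.**
- By prior radiation alone: Arm 1 is all EBRT-only patients; Arm 2 is all brachytherapy patients.
- By the Arm 2 line in 3.8.2: Arm 1 is EBRT-only patients without tumor outside imaging; Arm 2 is brachytherapy patients plus the remaining EBRT-only patients.

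Arm 1 is EBRT-only either way. It is Arm 2 that becomes mixed. Section 3.1.1 shows the same looseness: it counts late injuries within a cohort but stops escalation in an arm. The two coincide only if arm follows prior radiation.

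**Related wording.** Read literally, 2.3.1 lets a patient with EBRT plus temporary brachytherapy meet both cohort definitions, because Cohort 1 excludes only permanent brachytherapy and Cohort 2 takes any. Sections 3.1 and 10.4.1 put him with the brachytherapy patients.

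**The case against.** The best defence is that the operative rule is clear. The section meant for assignment states it without exception, and 3.1, 10, 10.4.1 and the prescription sentence in 3.8.2 agree. Against them stand a sentence fragment in a contouring section and a background paragraph. That is a fair account of the weight of text. It does not remove the conflict: the fragment sits directly under the Arm 2 heading in the section used for treatment planning, 1.2.4 describes the same two groups, and no passage gives an order of precedence.

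Several stronger readings are tempting, and the documents do not support them.

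- *All EBRT patients are affected.* They are not. EBRT with brachytherapy is Cohort 2, and EBRT-only patients without tumor outside imaging are Arm 1 throughout.
- *Arm 1's MTD could be undone.* Section 1.2.5 reports two Arm 1 participants at level 2 with Grade 3 urinary toxicity, which equals the late bladder threshold of 2 in 3.1.1. A reader might infer that moving one to Arm 2 leaves a count of 1. But 1.2.5 places both in Arm 1, gives no biopsy pattern, and does not suggest that either received the gland dose. Toxicity belongs with the regimen delivered.
- *Neither arm describes a defined population.* Arms are defined by the treatment given, and Arm 1 stays EBRT-only. Arm 2 would be heterogeneous, not undefined.
- *Further escalation decisions are at risk.* Level 3 is closed in both arms, and 1.2.5 rests the decision not to escalate Arm 2 on outside literature and disease control, not on a DLT count.
- *A given share of Arm 1 is in dispute.* An assumed 10% to 30% of the 21-patient arm maximum gives 0.10 × 21 = 2.1 to 0.30 × 21 = 6.3 patients. No document figure anchors that share, and the 21 is a whole-arm maximum that cannot be set against dose groups of 3 to 6.

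**Conclusion.** The inconsistency is real and stands in the current text. For an EBRT-only patient with biopsy-positive disease outside the imaged lesion, the protocol gives two incompatible answers on arm and whole-prostate dose, and 3.8.2 contains both. The size per patient is known: no prescribed prostate dose against 30 Gy in 5 fractions, and a place in one arm's toxicity count or the other's. The number of such patients is not given, and nothing shows that an EBRT-only patient was treated in Arm 2.

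With escalation closed, what remains is which treatment such a patient receives, including in expansion, and whether Arm 2 toxicity, and biochemical progression-free survival (bPFS) where reported by arm, describe brachytherapy patients only or a mixture. The conclusion rests on comparing texts and needs no assumed rate. The Cohort 1 brachytherapy wording is a minor slip, largely answered by 3.1 and 10.4.1.

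**What to change.** Reconcile Sections 1.2.4, 2.3.1, 3.1 and 3.8.2 into one assignment rule that gives each patient exactly one cohort and one arm, and that states explicitly what happens when biopsy shows tumor outside the imaged area. Which rule is right is a clinical decision for the sponsor and the investigator; this review takes no position on it. Align the Cohort 1 brachytherapy wording in 2.3.1 with 3.1 and 10.4.1 in the same amendment.

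Check the records for any EBRT-only patient who has already received the whole-prostate dose. If there is one, add to Section 10.4 a listing of such patients, and report Arm 2 toxicity and bPFS with and without them, keeping each toxicity with the regimen actually delivered. If there is none, a sentence saying so is enough.

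The cost is amendment wording, a records check and, only if needed, one listing and one sensitivity table.

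### For a man with prior EBRT only and biopsy tumour outside the imaged lesion, the protocol gives two incompatible answers on arm and whole-prostate dose, so the arm that counts his DLT is undetermined

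*Combined protocol and SAP*

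**What the plan says.** Two rules stand in the current text.

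**By prior radiation alone.** Section 2.3.1 defines Cohort 1 as "Patients with locally recurrent prostate cancer after treatment with EBRT. These patients cannot have had permanent brachytherapy as part of their treatment" and adds "Subjects in Cohort 1 will be directly assigned to Arm 1". Of Cohort 2 it says "These patients must have had brachytherapy as part of their treatment", and then "Subjects in Cohort 2 will be directly assigned to Arm 2". Biopsy location plays no part. Section 3.1 gives one reason for the gland dose: "The low dose total prostate exposure is used in Arm 2 as MR imaging may be moderately compromised in after prior brachytherapy". Section 10 also bases the arm on prior radiation. Section 10.4.1 describes the arms in the same way, although it numbers them in the reverse order.

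**By prior radiation or biopsy finding.** Section 1.2.4 reserves the reduced dose to the rest of the gland for two groups: "those who have biopsy findings consistent with disease outside of the imaging identified lesion and patients who have undergone prior brachytherapy". Under its Arm 2 heading, section 3.8.2 states the entry condition as "Brachytherapy or tumor (Gleason > or = to 6) identified in regions outside of areas defined by imaging".

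Section 3.8.2 then returns to the first rule for the prescription: "Dose to PTV prostate (cohort 2 only) will be prescribed to 30 Gy in 5 fractions". Tables 2 and 4 give Arm 1 no prostate dose and Arm 2 30 Gy.

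Section 3.1.1 sets the MTD for each arm separately. Section 3.1.2 escalates the arms independently because toxicity is expected to depend on prior treatment.

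**The concern.** Systematic biopsies are part of baseline (2.4, 3.1, 3.7) and sample outside the imaged lesion. A positive core there in a man with EBRT only is therefore a foreseeable finding. Two staff members, each following the protocol, could put this man in different arms and plan different whole-prostate doses for him.

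The primary endpoint is also involved. It is a separate MTD for each arm, read from very small counts. If some of these men are handled under one rule and some under the other, the arms no longer correspond to the prior-treatment groups that 3.1.2 meant to keep apart. The late-toxicity rule in 3.1.1 has the same weakness: it counts events within a cohort but stops escalation within an arm. If cohort there has its 2.3.1 meaning, the rule works only while cohort and arm coincide, and the second route into Arm 2 breaks that match.

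**Working it through.** The plan states no figure for this point, so there is none to reproduce. The check compares the texts, followed by a short calculation of how far the counts could move.

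**Step 1. Apply each text to one man.** He had EBRT only, and a systematic core shows tumour of Gleason 6 or more outside the imaged lesion.

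| Text | Criterion used | Result for him |
|---|---|---|
| 2.3.1 | Prior radiation | Cohort 1, Arm 1, no prostate dose |
| 3.1 | Prior radiation | Arm 1, no prostate dose |
| 10 | Prior radiation | Same basis as 2.3.1 |
| 3.8.2, prescription sentence | Membership of Cohort 2 | No 30 Gy |
| 3.8.2, Arm 2 entry line with Table 4 | Brachytherapy or off-image tumour | Arm 2, 30 Gy to the prostate |
| 1.2.4 | Off-image biopsy disease or brachytherapy | Reduced dose to the rest of the gland |

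Section 1.2.4 names neither Arm 2 nor 30 Gy, but 30 Gy in Arm 2 is the only gland dose in Tables 2 and 4. He cannot be moved into Cohort 2 to remove the conflict, because 2.3.1 makes brachytherapy a condition of entry to it. No text ranks the two rules or provides for a change of arm.

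**Step 2. Link to the MTD.** Under 3.1.2 a level is tolerated with at most 1 DLT among up to 6 patients, and exceeded with 2. If one man with a DLT is added to an arm whose level has 1 DLT, the count is 1 + 1 = 2 and the classification changes. If he is taken from a level with 2, the count is 2 − 1 = 1 and it changes the other way.

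The recorded decisions rest on counts of this size. Section 1.2.5 bases the Arm 1 decision on 2 participants with Grade 3 urinary events at level 2, and the late-toxicity rule in 3.1.1 needs 2 patients. If either man belonged to the other arm, 2 − 1 = 1 would fall short. The Arm 2 expansion rests on 3 men at each of two levels. The documents do not say whether any of these men had off-image tumour.

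**Step 3. How often the case could arise (assumed shares).** The documents give no share q of men with EBRT only who have off-image biopsy tumour. The range of 5% to 40% is an assumption.

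- Chance that a six-man Arm 1 level holds at least one such man: 1 − (1 − q)^6.
- Expected number among 21 (the Arm 1 maximum in 10.2): 21 × q.

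| q (assumed) | At least one in 6 | Expected in 21 |
|---|---|---|
| 5% | 1 − 0.95^6 = 27% | 1.1 |
| 10% | 1 − 0.90^6 = 47% | 2.1 |
| 20% | 1 − 0.80^6 = 74% | 4.2 |
| 40% | 1 − 0.60^6 = 95% | 8.4 |

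Section 10.2 itself says that its sample size is probably over-estimated, so the last column is an upper illustration. These figures count men whose arm is in dispute. They are not the chance that an MTD changes, which also requires a DLT in such a man.

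**The case against.** The strongest reply is that the protocol does have a rule. Section 2.3.1 is the only section devoted to treatment assignment and is unambiguous. Sections 3.1 and 10 agree with it, and so does the prescription sentence of 3.8.2. Against them stand one sentence in the background and one line without a verb. This has weight: the prior-radiation reading is the better supported. It does not settle the matter. The line without a verb stands in the target-volume section, where treatment is planned. It carries its own Gleason threshold, which suggests a deliberate criterion, and it agrees with 1.2.4.

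A second reply is that dose escalation has ended in both arms (1.2.5, notes to Tables 2 and 4), so no further escalation decision depends on this. That is correct and limits the point. What remains is the classification of men already treated, the expansion patients, and the MTD that is reported.

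A third reply is that moving men between arms changes a 3+3 decision only if they had DLTs. That also stands: moving a man without a DLT cannot turn a tolerated level into an exceeded one.

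A reader might infer that in Arm 1 the off-image tumour is knowingly left without dose. The documents do not establish this. The Arm 1 GTV in 3.8.2 is defined by imaging, but the précis speaks of areas shown on biopsy or advanced imaging, and 2.3.1 and 3.1 name both imaging and biopsy. Whether such an area is an Arm 1 target is a separate open question, and answering it would not settle the arm.

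**Conclusion.** The contradiction is real, lies in current operative text and includes one within 3.8.2 itself. For one foreseeable kind of patient, the arm, the whole-prostate dose and the arm that counts his DLT are undetermined. This rests on the wording alone and on none of the assumed shares.

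The possible effect is large per patient, since one reclassified man with a DLT can move a level across the boundary between 1 and 2. Its actual size is unknown, because the documents neither give the frequency nor show that any treated man is affected. It would go too far to conclude that either recorded MTD decision is wrong.

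A reader might also infer that bPFS by arm is distorted. Sections 1.1.2, 10.1 and 10.4.3 specify no bPFS analysis by arm, so the documents support the consequence for DLTs and the MTD only. Nor does it follow that DLTs must be counted by treatment delivered: that would put post-EBRT men into Arm 2 whenever they received the gland dose, and so create the mixture of prior treatments that 3.1.2 seeks to avoid.

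The passages should be reconciled before further expansion patients are assigned and before the MTD is reported.

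**What to change.** 1. Reconcile 1.2.4, 2.3.1, 3.1, 3.8.2 (both the Arm 2 entry line and the prescription sentence) and 10, so that one rule decides arm and whole-prostate dose. Which rule is a clinical choice for the sponsor. Align the arm numbering in 10.4.1 at the same time.
2. For each treated patient, record the prior radiation, the prostate dose delivered, and the criterion that led to it (brachytherapy or off-image biopsy tumour).
3. State in 3.1.1 or 10.4.1 which arm counts the DLT of a man whose arm differs between the two readings, and give the reason.
4. Report DLT counts and the resulting MTD per arm and dose level, with and without these men, showing the denominators. If there are none, say so; the matter is then closed for the patients already treated.

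The cost is a wording amendment, one derived variable from existing biopsy and planning records, and one extra table. It needs no additional patients or procedures.
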